### **5 Levels of Significance**

No hypotheses are specified for this study and no p-values are being calculated, therefore no level of significance is specified. All estimation of endpoints will be performed using 95% confidence intervals.

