## 8.4 Primary and Secondary Endpoints and Associated Hypotheses

### 8.4.1 Primary Endpoint and Associated Hypotheses

No formal hypotheses are specified for this study. The study endpoints are representative of endpoints that are currently reported in the available literature for similar energy devices and this will allow for qualitative comparisons with the results from this study.

The primary performance endpoint in this study is the percentage of vessels where hemostasis ( $\leq$  Grade 3) is achieved using the ENSEAL X1 device and no additional hemostatic products (e.g., hemoclips, staples, sutures, fibrin sealants, other advanced energy) are needed to obtain hemostasis. The hemostasis grading scale applied is defined as:

- Grade 1: no bleeding at transection site;
- Grade 2: minor bleeding at transection site, no intervention needed;
- Grade 3: minor bleeding at transection site, mild intervention needed, use of monopolar device and/or touch-ups with ENSEAL X1;
- Grade 4: significant bleeding (e.g., pulsatile blood flow, venous pooling) requiring intervention such as extensive coagulation or ligation with additional hemostatic products (e.g., hemoclips, staples, sutures, fibrin sealants, other advanced energy products).

The primary performance endpoint will be summarized at the transection level as multiple transections per subject are expected; that is, the denominator for the primary endpoint will be the total number of transections and the numerator will be the number of transections where hemostasis ( $\leq$  Grade 3) was achieved. An exact 95% confidence interval using the Clopper-Pearson method will also be estimated. Primary performance endpoint summaries will be provided for each procedure group and in total.

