### 8.4.2 Secondary Endpoints and Associated Hypotheses

Counts and percentages will be provided for the following endpoints:

- type and number of vessels transected;
- grading scale distribution for all vessels transected;
- tissue sticking score of vessel transection;
- number of times compression was used for Grade 3 interventions;
- number of times monopolar device touch-ups were required for Grade 3 interventions; and,
- number of times ENSEAL X1 touch-ups were required for Grade 3 interventions.

The protocol identifies an additional endpoint of ‘the number of times additional hemostatic product was required to obtain hemostasis for Grade 4 bleeding’. Given the low number of Grade 4 ratings that have been observed in the trial at the time of finalization of this SAP, no summaries will be performed for this endpoint, and only a data listing will be generated.

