### 8.8 Sensitivity Analyses

The analysis of the primary performance endpoint described above in Section 8.4.1 makes the assumption of independence of transections within a subject in estimation of variance for the confidence interval calculation. To account for the potential dependence among transections within a subject, a sensitivity analysis will be performed where the 95% confidence interval will be estimated using a bootstrap approach. For each subject, the outcome of all transections will be represented by a vector of 1’s (indicating a score of  $\leq$  Grade 3 hemostasis) and 0’s (indicating a score of Grade 4 hemostasis). This vector will be re-sampled with replacement to generate a bootstrap sampled vector of observations for each subject. Then, the proportion of observations

scored as  $\leq$  Grade 3 hemostasis for each subject will be calculated from this bootstrap vector. After obtaining a sample proportion of transections achieving  $\leq$  Grade 3 hemostasis for each subject, the mean of these sample proportions will be calculated across all subjects to provide an estimated sample proportion of transections achieving  $\leq$  Grade 3 hemostasis based on 1 iteration of the bootstrap process. This process will then be repeated a minimum of 5000 times to generate a sampling distribution for the proportion of transections achieving  $\leq$  Grade 3 hemostasis. The mean of this sampling distribution will be provided as the point estimate of the proportion of transections achieving  $\leq$  Grade 3 hemostasis and the 95% confidence interval will be estimated by the lower 0.025 and upper 0.975 percentiles of this sampling distribution.

The table below demonstrates 1 iteration of this bootstrap process.

Subject ID	Observed Data Vector	Bootstrap Sampled Vector	Bootstrap-Based Sample Proportion
1	(1, 1, 0, 1, 1)	(1, 0, 1, 0, 1)	0.60
2	(1, 1, 1)	(1, 1, 1)	1.0
3	(1, 0, 1, 1)	(0, 1, 1, 1)	0.75
4	(1, 1, 0, 1, 1)	(1, 1, 1, 1, 1)	1.0
5	(1, 1)	(1, 1)	1.0
...	...	...	...
...	...	...	...
N	(0, 1, 1, 0, 1)	(1, 0, 1, 1, 1)	0.80
Summary			Mean of above proportions to get 1 observation in the sampling distribution of the proportion of transections achieving $\leq$ Grade 3 hemostasis.

The above re-sampling process will then be repeated a minimum of 5000 times to estimate the sampling distribution.

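### SAP 8.8's percentile bootstrap gives a 95% interval of 100% to 100% for any column with no Grade 4 transection, and the SAP has no rule for that case

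*SAP*

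**What the plan says.** SAP 5 makes intervals the study's only inferential output: there are no hypotheses or p-values, and "All estimation of endpoints will be performed using 95% confidence intervals".

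For the primary endpoint, SAP 8.4.1 counts transections and treats Grade 3 or lower as success. It adds: "An exact 95% confidence interval using the Clopper-Pearson method will also be estimated". On the level of reporting it says: "Primary performance endpoint summaries will be provided for each procedure group and in total".

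SAP 8.8 acknowledges that this interval treats transections as independent. It continues: "To account for the potential dependence among transections within a subject, a sensitivity analysis will be performed". Each subject's transections are coded 1 (Grade 3 or lower) or 0 (Grade 4). Then "This vector will be re-sampled with replacement to generate a bootstrap sampled vector of observations for each subject", and "the mean of these sample proportions will be calculated across all subjects". After at least 5000 repetitions, "the 95% confidence interval will be estimated by the lower 0.025 and upper 0.975 percentiles of this sampling distribution".

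SAP 8.8 does not mention procedure groups and has no rule for data without a 0. Its worked table shows a 0 in the observed vector of four of the six subjects displayed, so it does not illustrate sparse failures. Yet SAP 8.4.2 drops the summary of additional hemostatic products in favour of a listing, and gives as its reason: "Given the low number of Grade 4 ratings that have been observed in the trial". It gives no count and no split by group.

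**The concern.** A percentile bootstrap can only redraw values that were observed. If a column contains no 0, every replicate equals 1, and no number of iterations changes that. The interval has zero width and excludes every true success rate below 100%.

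The error runs in the wrong direction. SAP 8.8 exists because the Clopper-Pearson interval may be too narrow when transections within a subject are correlated. An analysis that allows for dependence should not claim more certainty than one that ignores it. In a column with no failures it would claim complete certainty, and could be read as showing that dependence does not matter.

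This is separate from the choice of resampling unit. Resampling whole subjects does not help, because every subject's vector is all 1s.

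**Working it through.** **Inputs**
- Minimum transections: 60 colectomy, 60 gynecological, 40 thoracic, at least 200 in total (SAP 7, from an expected minimum of two vessels per procedure).
- Minimum subjects: 30, 30 and 20, with 100 in total (SAP 1.2).
- True Grade 4 rate: not given. Assumed at 1%, 2% and 3%.
- Transections per subject above the minimum: not given. A value of 5 is assumed as the contrast, giving 150, 150 and 100.

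**Step 1. The plan's own figures.** The SAP gives none for the bootstrap. Its SAP 7 figures reproduce: 1 − 0.98^100 = 86.7%, and the exact two-sided upper limit for 0 of 100 is 1 − 0.025^(1/100) = 3.62%, consistent with the stated bound of 3.7%.

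**Step 2. The collapse.** If all values are 1, every subject proportion is 1, every replicate mean is 1, and both percentiles are 1. The SAP 8.8 scheme was coded as written, with four variants: resampling subjects with a mean of proportions, resampling subjects with a ratio of totals, resampling pooled transections, and a two-stage bootstrap. On all-success data of 20, 30 and 100 subjects with two vessels each, all five gave 100% to 100%.

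**Step 3. What an exact interval gives instead.** With n successes in n, the Clopper-Pearson lower limit is 0.025^(1/n).

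| Column (minimum size) | Transections as n | Subjects as n | Bootstrap |
|---|---|---|---|
| Colectomy or gynecological | 60/60: 94.0% | 30/30: 88.4% | 100% |
| Thoracic | 40/40: 91.2% | 20/20: 83.2% | 100% |
| Total | 200/200: 98.2% | 100/100: 96.4% | 100% |

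Transections as n corresponds to independence, and subjects as n to complete within-subject dependence. A lower limit that allows for dependence should lie between the two.

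**Step 4. How often a group is empty of Grade 4.** Assume independent transections with a common rate q, and a bootstrap run by group. With n transections, P(no Grade 4) = (1 − q)^n. For two groups of size a and one of size b,

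P(at least one empty group) = 1 − [1 − (1 − q)^a]² × [1 − (1 − q)^b].

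At q = 1% with 60/60/40: 0.99^60 = 0.547 and 0.99^40 = 0.669, so 1 − 0.453² × 0.331 = 93%.

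At q = 1% with 150/150/100: 0.99^150 = 0.221 and 0.99^100 = 0.366, so 1 − 0.779² × 0.634 = 62%.

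| Grade 4 rate | 60/60/40 | 150/150/100 | Pooled 200: P(none) |
|---|---|---|---|
| 1% | 93% | 62% | 13% |
| 2% | 73% | 21% | 1.8% |
| 3% | 50% | 7% | 0.2% |

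Positive clustering within subjects would raise the chance of an empty group at a given rate.

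**The case against.** The algebra is not in dispute. The case on the other side concerns likelihood and consequence, and much of it stands.

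- **By-group use is inferred.** SAP 8.8 averages across all subjects and names no groups; the by-group sentence is in SAP 8.4.1. This stands, and it is why the probabilities above are conditional. By-group use remains the natural reading for a check on a by-group result.
- **The pooled total.** A reader might infer that the whole-study interval will collapse. The documents do not support that. SAP 8.4.2 calls the Grade 4 count low and plans a listing, which implies that some had been seen. One Grade 4 vessel anywhere rules out 100% to 100% for the total.
- **Near-certainty of an empty group.** A reader might take 93% as the forecast. It rests on minimum counts, before the 20 floating subjects are allocated, and on an assumed rate. At 5 transections per subject an empty group is more likely than not only at rates near or below 1%.
- **Display and decisions.** A reader might picture the zero-width interval printed beside the primary result. Table 7 has one confidence-interval row, and no shell shows a bootstrap result. The Clopper-Pearson interval remains primary, comparisons with the literature are qualitative, and no decision rule uses the bootstrap. A 100% to 100% interval is also visibly degenerate.
- **A larger weakness lies nearby.** Because SAP 8.8 keeps subjects fixed, its interval is also too narrow when a few Grade 4 vessels exist. With 3 in 200, in three different subjects, it gave 97.5% to 99.5%, against 95.7% to 99.7% by Clopper-Pearson. That is true, but it is a separate fault, and resampling subjects would not cure the present one.

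**Conclusion.** The point holds as a defect of the sensitivity analysis. Followed as written, SAP 8.8 returns a zero-width interval for any column with no Grade 4 transection. That conclusion needs no assumption. At the minimum group sizes the lower limit would read 100%, where exact limits run from 88.4% to 94.0% (colectomy or gynecological) and from 83.2% to 91.2% (thoracic).

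Whether it will happen depends on three things that the documents leave open: by-group use, the Grade 4 rate, and the number of transections per subject. Under by-group use and independence, an empty group is plausible: 50% to 93% at minimum counts and 7% to 62% at 5 per subject, for rates from 3% down to 1%. Collapse of the pooled total is unlikely. The primary result is unaffected, so this warrants a correction to SAP 8.8 but does not undermine the study's main estimate.

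**What to change.** Add two statements to SAP 8.8:

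1. The sensitivity interval is produced for each procedure group and in total.
2. For any column with no Grade 4 transection, the bootstrap interval is not reported. An exact Clopper-Pearson interval is given instead, with the number of subjects who contributed at least one transection to that column as the denominator, labelled as the full-dependence bound.

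Counting only contributing subjects matters because SAP 6 also admits subjects in whom the device was used only for cutting or dissection. SAP 7 already takes an exact limit on subjects for its zero-event safety example, so the method is not new to the plan. An effective sample size from an estimated design effect is less suitable: with a handful of Grade 4 vessels the estimate is unstable, and with none in the whole study there is nothing to estimate it from.

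The cost is two sentences and a few lines of code, with no new data. The price is a wider, less favourable sensitivity interval in the affected columns. If the SAP is already final, SAP 8.1 requires the change to be identified in the output and documented in the study report.

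This rule does not cure the narrowness that comes from holding subjects fixed when a few Grade 4 vessels exist; that needs its own correction.

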## 8.9 Subgroup Analysis

Subgroup analyses of the primary performance endpoint are planned to be performed for the subgroup of subjects who have a medical history of treatment for cancer (chemotherapy or radiation as identified on the Background Information 2 eCRF) and the subgroup of subjects with potentially compromised vessel condition (presence of inflamed tissue or calcified tissues/vessels as identified on the Intra-operative Data eCRF). Similar subgroup analyses will also be performed by named vessel types. Upon completion of data entry into the study database, entries into the free text field for named vessels will be grouped into similar categories, e.g. short gastric or right/left uterine, and summaries of the primary performance endpoint will be generated for these subgroups.

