3.4.2 Surgical Variables

The following will be recorded preoperatively, intraoperatively, or postoperatively:

- Date/time of hospital admission;
- Procedure duration, defined as first incision to final closure;
- Did vessel skeletonization occur (Yes/No; if Yes, describe);
- Was there presence of inflamed tissue or calcified tissues/vessels, if applicable (Yes/No; if Yes, describe);
- Volume of estimated intra-operative blood loss;
- For each vessel transected with ENSEAL X1 (only the PI or sub-Investigator can use the device):
 - Name of each vessel;
 - Hemostasis grading scale assessment;
 - Tissue sticking – graded using a 4-point Likert scale (Appendix I);
 - For every Grade 3 vessel transection:
 - Touch-ups with a monopolar device, if applicable (Yes/No; if Yes, record number of touch-ups);
 - Touch-ups with ENSEAL X1 (Yes/No; if Yes, record number of touch-ups);
 - For every Grade 4 vessel transection intervention (additional hemostatic product was used to obtain hemostasis on vessels [e.g. hemoclips, staples, sutures, fibrin sealants, other advanced energy products]):
 - Type, name, and number of times used for each additional hemostatic product used;
- For the gynecological procedure group, if applicable:
 - Uterine size; and
 - Summary of histological diagnoses including fibroids (subserosal, intramural, submucosal), adenomyosis, endometriosis, endometrial abnormality, or other, specify;
- Chest tube data, if applicable:
 - Number of chest tubes placed;
 - Date(s) of chest tube placement and removal;
 - Daily volume and characteristics of chest tube(s) drainage;
- Occurrence of blood transfusion, if applicable (record the total required units of blood and rationale);
- Occurrence of ENSEAL X1 used for tissue cutting or dissection (Yes/No; if Yes, describe including description of tissue cut/dissected);
- Concomitant procedures, if applicable (defined as any medical or surgical procedure beyond activities associated with primary study procedure type). If a

concomitant procedure requires vessel transection by ENSEAL X1, each vessel transected will have the same information captured as stated above for vessel transections;

- Concomitant medication usage associated with AEs; and
- Date/time of hospital discharge.

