4.5.4 Primary and Secondary Endpoints and Associated Hypotheses

All study endpoints are described in Section 2.1 through Section 2.4. No formal hypotheses are specified for this study. The study endpoints are representative of endpoints that are currently reported in the available literature for similar energy devices and this will allow for comparisons with the results from this study. There also will be a stratification of vessel sealing based on medical history, named vessel type, and vessel condition.

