Denominator and percentages are based on number of vessels transected in each group.

*Programming notes:*

1. Only records indicated as “Original procedure” will be summarized in this table.
2. For number of vessels using touch up questions, the number presented will be the number of times “yes” is answered to the corresponding CRF question (VTMONO or VTENS); For summary statistics on number of touch-ups, the variables VTTUP and VTTUPS will be summarized

The following tables will have the same format as Table 7:

Table 8	Vessel Transection Summary – Original Procedure ENSEAL Analysis Set Subjects With Medical History for Treatment of Cancer
Table 9	Vessel Transection Summary – Original Procedure ENSEAL Analysis Set Subjects With Presence of Inflamed Tissue or Calcified Tissues/Vessels
Table 10.1	Vessel Transection Summary – Original Thoracic Procedures ENSEAL Analysis Set Vessels Identified as Short Gastric Vessels
Table 10.2	Vessel Transection Summary – Original Gynecological Procedure ENSEAL Analysis Set Vessels Identified as Right Uterine Vessels
Table 10.3	Vessel Transection Summary – Original Gynecological Procedure ENSEAL Analysis Set Vessels Identified as Left Uterine Vessels
Table 10.4	Vessel Transection Summary – Original Gynecological Procedure ENSEAL Analysis Set Vessels Identified as Right Ovarian Vessels
Table 10.5	Vessel Transection Summary – Original Gynecological Procedure ENSEAL Analysis Set Vessels Identified as Left Ovarian Vessels
Table 10.6	Vessel Transection Summary – Original Thoracic Procedure ENSEAL Analysis Set Vessels Identified as Left Gastroepiploic Vessels
Table 10.7	Vessel Transection Summary – Original Gynecological Procedure ENSEAL Analysis Set Vessels Identified as Omental Vessels
Table 10.8	Vessel Transection Summary – Original Colectomy Procedure ENSEAL Analysis Set Vessels Identified as IMA Vessels

Note: Tables 10.1 through 10.8 will only present a column for the identified procedure in the Table title.

Table 11  
 Device Procedure Questionnaire  
 ENSEAL Analysis Set

Characteristic	Colectomy (N = ##)	Gynecological (N = ##)	Thoracic (N = ##)	Total (N = ##)
Number of Hands Required				
One Hand	xx (xx.x%)	xx (xx.x%)	xx (xx.x%)	xx (xx.x%)
Two Hands	xx (xx.x%)	xx (xx.x%)	xx (xx.x%)	xx (xx.x%)
Repositioning or Adjustment Needed?				
Yes	xx (xx.x%)	xx (xx.x%)	xx (xx.x%)	xx (xx.x%)
No	xx (xx.x%)	xx (xx.x%)	xx (xx.x%)	xx (xx.x%)
Need to Change Hand Positions to Activate ENSEAL X1?				

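### Vessel condition is recorded once per procedure but applied to every transection, so SAP Table 9 mixes affected and unaffected vessels and cannot give the stratification by vessel condition that the protocol promises

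*SAP*

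**What the plan says.** Protocol 4.5.4 states: "There also will be a stratification of vessel sealing based on medical history, named vessel type, and vessel condition". Sealing is graded vessel by vessel, and SAP 8.4.1 fixes the unit of the primary endpoint: "the denominator for the primary endpoint will be the total number of transections".

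Protocol 3.4.2 collects condition through a single procedure-level question: "Was there presence of inflamed tissue or calcified tissues/vessels, if applicable (Yes/No; if Yes, describe". This stands apart from the per-vessel block, which opens "For each vessel transected with ENSEAL X1 (only the PI or sub-Investigator can use the device" and covers vessel name, hemostasis grade, tissue sticking, Grade 3 touch-ups and Grade 4 products. That block has no condition item.

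SAP 8.9 defines the subgroup by subject, as "the subgroup of subjects with potentially compromised vessel condition", and takes the flag from the procedure form: "presence of inflamed tissue or calcified tissues/vessels as identified on the Intra-operative Data eCRF". SAP Table 6 tabulates the same item by subject. In the SAP appendix, Table 9 is headed "Subjects With Presence of Inflamed Tissue or Calcified Tissues/Vessels" and takes the format of Table 7, whose footnote reads "Denominator and percentages are based on number of vessels transected in each group". A programming note limits these tables to records from the original procedure. No table is listed for subjects who answered No.

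**The concern.** A subject-level flag is being used to stratify a vessel-level outcome. A subject with one inflamed or calcified site contributes all of his or her transections to Table 9, including those through unaffected vessels. The question also covers inflamed tissue in general, so a Yes need not concern any vessel that was transected.

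Table 9 is the only planned summary by observed tissue or vessel condition. If condition worsens sealing, the mixing pulls Table 9 towards the result in unaffected vessels, which favours the device. Because no table for the No stratum is planned, the natural comparator is Table 7. That table contains the same flagged subjects, which narrows the visible difference further.

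**Working it through.** **Figure in the plan.** The sample-size sections (Protocol 4.5.7, SAP 7) expect at least 2 transections per procedure and at least 200 in total. Check: 2 × (30 + 30 + 20 + 20) = 2 × 100 = 200. The figure reproduces. The worked example in SAP 8.8 shows subjects with 2 to 5 transections.

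**Notation.**
- q = share of flagged subjects' transections that are truly affected (not in the documents).
- p_u, p_a = hemostasis rates in unaffected and affected vessels (not in the documents).
- f = share of all transections that come from flagged subjects (not in the documents).

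Assume that unflagged subjects have only unaffected vessels, and that unaffected vessels have the same rate p_u in flagged and unflagged subjects.

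**Step 1: rate shown in Table 9.** R = q·p_a + (1 − q)·p_u.

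**Step 2: difference from unflagged subjects.** p_u − R = q·(p_u − p_a). The true difference is multiplied by q, whatever the two rates are.

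**Step 3: difference from the Table 7 total.** The total is f·R + (1 − f)·p_u. Subtracting R gives (1 − f)·q·(p_u − p_a).

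**Step 4: q when exactly one vessel per flagged subject is affected.** The fraction of the difference retained is 1/2 with 2 transections, 1/3 with 3, 1/4 with 4 and 1/5 with 5. If every transected vessel is affected, q = 1 and nothing is lost.

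**Step 5: illustration.** The rates are assumed: p_u = 98% and p_a = 90%, a true difference of 8.0 points.

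| q | Table 9 hemostasis rate | Difference from unflagged |
|---|---|---|
| 1 | 90.0% | 8.0 points |
| 2/3 | 92.7% | 5.3 points |
| 1/2 | 94.0% | 4.0 points |
| 1/3 | 95.3% | 2.7 points |
| 1/5 | 96.4% | 1.6 points |

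Against the Table 7 total at q = 1/2:
- f = 0.1: 0.9 × 0.5 × 8.0 = 3.6 points
- f = 0.3: 0.7 × 0.5 × 8.0 = 2.8 points
- f = 0.5: 0.5 × 0.5 × 8.0 = 2.0 points

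Even with perfect classification (q = 1), comparison with the total at f = 0.3 would show 0.7 × 8.0 = 5.6 points rather than 8.0. That is a separate reason to print the No stratum.

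**The case against.** The sponsor has several fair answers.

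- **The labelling is cautious.** SAP 8.9 speaks of subjects and of potential compromise, and the Table 9 title also says subjects. A reader might infer that the SAP labels healthy vessels as compromised. It does not. What stands is that this subject-level table is the only output for the protocol's vessel-condition stratum.
- **Protocol 4.5.4 sets no unit.** Results in patients with an inflamed or calcified operative field are a legitimate descriptive question. They are still a different question from sealing by vessel condition.
- **No contrast is planned.** There are no hypotheses or p-values, and Protocol 4.5.9.7 calls subgroup analyses exploratory. This limits the consequence, but a stratification is of little use unless strata can be compared.
- **The size is unknown.** A reader might infer from the one-affected-vessel cases that 50% to 80% of the difference is lost. That requires q between 1/5 and 1/2, which the documents do not support. The colectomy indications in SAP Table 4.1 include ulcerative colitis, Crohn's disease and diverticulitis, where several sites could be inflamed and q could be near 1.
- **Diluted is not the same as hidden.** A reader might infer that diseased vessels would look as good as healthy ones. Under the illustrative rates, Table 9 would still show 3.6% to 6.0% Grade 4 for q from 1/5 to 1/2, against 2% in unaffected vessels.
- **Other difficult-tissue summaries exist.** Table 8 covers prior cancer treatment, and Tables 10.1 to 10.8 cover named vessels. Neither uses observed condition.
- **Events are sparse.** SAP 8.4.2 reports few Grade 4 ratings, so imprecision may limit Table 9 more than dilution does.

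**Conclusion.** The mismatch of levels is clear from the two documents and holds. Table 9 pools affected and unaffected vessels, and any true effect of condition appears at q times its size against unflagged subjects, and smaller still against Table 7. The multiplier ranges from 1 (all transected vessels affected) through 1/2 (one of two affected) to lower values when more vessels are transected. Where it falls in this study cannot be derived from the documents.

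The conclusion assumes that condition affects hemostasis and that some transected vessels in flagged subjects are unaffected. If either is untrue, there is no dilution. The primary endpoint and its confidence interval are not touched. This is a low-cost improvement to an exploratory table, not a flaw in the main analysis.

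**What to change.** **If vessel records can still be changed:** add a Yes/No item to each Vessel Transected record asking whether the transection site was inflamed or calcified, answered before the seal is graded where possible. Define Table 9 by that field and show the No stratum beside it. Keep the procedure-level item for Table 6.

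**If the data are already collected:** SAP 8.4.2 shows that grades had been observed when the SAP was finalised, so this may be the practical case. Use the description text that accompanies a Yes to assign condition to named vessels, without sight of the hemostasis grade. The SAP already plans a similar free-text exercise for vessel names (8.9 and the note to Table 21). Whether the descriptions name vessels is not known from the documents.

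**Where the text does not allow this:** state that Table 9 is a subject-level summary of all original-procedure transections in subjects with any such tissue. Print the No stratum beside it, and do not present it as the vessel-condition stratification of Protocol 4.5.4.

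**Cost:** one extra entry per vessel, or a short masked text review, plus one further column or table. The new field would be rated by the operating surgeon and could be influenced by the seal result, which is why it should precede grading.
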